4.2. Extent of Study Drug Exposure and Adherence

4.2.1. **Duration of Exposure to Study Drug**

Duration of exposure to each study drug (E/C/F/TAF, F/R/TAF, LDV/SOF) will be defined as (last dose date – first dose date + 1), regardless of temporary interruptions in study drug administration, and will be expressed in weeks (recorded to 1 decimal place, eg, 4.5 weeks). If subjects are still on study drug, the latest of the study drug start dates and end dates, the clinical visit dates, and laboratory visit dates, excluding the 30-day follow-up visit date (and the post HCV treatment Week 4 and 12 visit dates and unscheduled visit dates for LDV/SOF only), will be used to imputed the last dose date for the calculation of the duration of study drug exposure.

Duration of exposure to study drugs will be summarized by treatment group for all study drugs and overall for LDV/SOF, using descriptive statistics (n, mean, standard deviation [SD], median, Q1, Q3, minimum, and maximum). In addition, for E/C/F/TAF and F/R/TAF, the number and percentage of subjects in the following categories will be summarized: ≥ 4 weeks (28 days), ≥ 8 weeks (56 days), ≥ 12 weeks (84 days), ≥ 16 weeks (112 days), ≥ 20 weeks (140 days), ≥ 24 weeks (168 days), and ≥ 32 weeks (224 days); for LDV/SOF, the number and percentage of subjects in the following categories will be summarized: ≥ 4 weeks (28 days), ≥ 8 weeks (56 days), and ≥ 12 weeks (84 days).

Summaries will be provided for HIV study drug using the Safety Analysis Sets, and for LDV/SOF using Part 2 Safety Analysis Set. No inferential statistics will be provided.

Time to premature discontinuation of HIV study drugs will be analyzed using the Kaplan-Meier (KM) method by treatment group, based on the Safety Analysis Sets. The log rank test will be used to compare the difference in study drug exposure between the two treatment groups.

4.2.2. Adherence to Study Drug

Study drug regimen adherence will be computed based on pill counts. The numbers of pills of study drug (E/C/F/TAF, F/R/TAF, or LDV/SOF) dispensed and returned are captured on Study Drug Accountability eCRF.

4.2.2.1. Adherence to HIV Study Drug

Adherence (%) of HIV study drug (E/C/F/TAF and F/R/TAF) will be calculated as follows:

Adherence (%) =
$$100 \times \frac{\text{Total No. of pills taken}}{\text{Total No. of pills prescribed}}$$

= $100 \times \frac{\sum \text{No. of pills taken at each dispensing period}^{[1]}}{\sum \text{No. of pills prescribed at each dispensing period}^{[2]}}$

- [1] Number of pills taken at a distinct dispensing period for a study drug is calculated as the minimum of (a) the daily number of pills prescribed for the study drug multiplied by the duration of treatment at the dispensing period of the same dispensing date, and (b) the number of pills taken for the study drug (number of pills dispensed minus the number of pills returned). Total number of pills taken is determined by summing the number of pills taken for each study drug contained in the study drug regimen from all evaluable dispensing periods.
- [2] Number of pills prescribed at a distinct dispensing period for a study drug is calculated as the daily number of pills prescribed for the study drug multiplied by the duration of treatment at the dispensing period of the same dispensing date. Total number of pills prescribed is determined by summing the number of pills prescribed for each study drug contained in the study drug regimen from all evaluable dispensing periods.

The duration of treatment at a dispensing period for a study drug is calculated as the minimum of (a) the last returned date of the same dispensing period for the study drug, (b) date of premature discontinuation of the study drug, and (c) next pill dispensing date of the study drug, minus dispensing date of the study drug.

The next pill dispensing date is the following dispensing date of the study drug regardless of the bottle return date.

For a record where the number of pills returned was missing (with "Yes" answered for "Was the Bottle returned?" question), it is assumed the number of pills returned was zero. If the number of pills dispensed was missing or any study drug bottle was not returned or the bottle return status was unknown for the same dispensing date, all records for the same dispensing date for that study drug will be excluded from both denominator and numerator calculation.

Descriptive statistics for overall and Week 24 adherence for HIV study drug (n, mean, SD, median, Q1, Q3, minimum and maximum) along with the number and percentage of subjects belonging to adherence categories (eg, < 80%, $\ge 80\%$ to < 90%, $\ge 90\%$ to < 95%, $\ge 95\%$) will be provided by treatment group and overall for subjects who return at least 1 bottle of HIV study drug and have calculable adherence during the study in the Safety Analysis Set. Week 24 adherence will be calculated from HIV drug dispensing records up to Week 24 (exclusive).

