8.1.3. Secondary Endpoint

Secondary efficacy endpoints are:

- SVR4 (HCV RNA < LLOQ 4 weeks after completion of LDV/SOF treatment).
- The proportion of subjects with HIV-1 RNA \geq 50 copies/mL (virologic failure) 24 weeks after start of the F/TAF-based regimen using FDA snapshot algorithm

Note: Most often, 24 weeks of HIV therapy will coincide with the Post-HCV Treatment Week 4 visit

Secondary safety endpoint is:

• Grades 1 through 4 adverse events after switch to E/C/F/TAF or F/R/TAF throughout the study and during coadministration with LDV/SOF treatment.

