3.4. Examination of Subject Subgroups

3.4.1. Subject Subgroups for Efficacy

The SVR endpoints SVR4 and SVR12 will be analyzed for the following subject subgroups:

- Age group ($< 65 \text{ years}, \ge 65 \text{ years}$) at Part 2 Baseline as defined in Section 3.8.1
- Sex (male, female)
- Race (black, non-black)
- Ethnicity (Hispanic or Latino, not Hispanic or Latino)
- HCV RNA ($< 800,000 \text{ IU/mL}, \ge 800,000 \text{ IU/mL}$) at Part 2 Baseline
- Body mass index (BMI, $< 30 \text{ kg/m}^2$, $\ge 30 \text{ kg/m}^2$) at Part 2 Baseline
- Alanine aminotransferase (ALT, ≤ 1.5 x ULN, ≥ 1.5 x ULN) at Part 2 Baseline
- Adherence to SOF/LDV (< 80%, $\ge 80\%$)
- Cirrhosis (presence, absence)
- Prior HCV treatment experience (treatment naive, treatment experienced)
- HCV study treatment status (completed, prematurely discontinued)

Statistical Analysis Plan – Final (SVR12) Analysis

The proportion of subjects with HIV-1 RNA < 50 copies/mL 24 weeks after the start of HIV study drug determined by the US FDA-defined snapshot algorithm {U. S. Department of Health and Human Services 2015} will be analyzed for the following subject subgroups (see Section 6.2.2.2 for details):

- Age (< 50 years, ≥ 50 years) at Study Baseline as defined in Section 3.8.1.
- Sex (male, female)
- Race (black, non-black)
- HIV study drug adherence (< 95%, ≥ 95 %; based on adherence up to Post HCV Treatment Week 4 visit)

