4.2.2.2. Adherence to LDV/SOF

The presumed total number of LDV/SOF tablets administered to a subject will be determined by the data collected on the drug accountability eCRF using the following formula:

Total Number of Doses Administered =
$$(\sum No. \text{ of } LDV/SOF \text{ Tablets Dispensed}) - (\sum No. \text{ of } LDV/SOF \text{ Tablets Not Administered})$$

The level of adherence to the study drug will be assessed based on the total amount of study drug administered relative to the total amount of study drug prescribed at LDV/SOF Day 1.

The level of adherence will be expressed in percentage using the following formula:

Level of Adherence (%) =
$$\left(\frac{\text{Total Amount of Study Drug Administered}}{\text{Total Amount of Study Drug Prescribed at Baseline}}\right) \times 100$$

Note: If calculated adherence is greater than 100%, the result will be set to 100%.

In this study, the total amount of LDV/SOF FDC (90 mg/400 mg) prescribed for 12 weeks will require 84 tablets.

Subjects who prematurely discontinue study drug for lack of efficacy (ie, virologic failure) will have the total amount of study drug prescribed calculated up to the first date when virologic failure criteria were met. For virologic failure confirmed by 2 consecutive measurements the date of the first measurement will be used. If there are study drug bottles dispensed on or after the subject first met virologic failure criteria, these bottles will not be included in the calculation of adherence. If a bottle is dispensed and the bottle is returned empty, then the number of tablets returned will be entered as zero. If a bottle is dispensed but not returned (missing), the number of tablets taken from that bottle will be counted as zero.

Descriptive statistics for the level of LDV/SOF adherence (n, mean, SD, median, Q1, Q3, minimum and maximum) with the number and percentage of subjects belonging to adherence categories (eg, < 80%, $\ge 80\%$ to < 90%, $\ge 90\%$) will be provided by treatment group and overall for the Part 2 Safety Analysis Set. No inferential statistics will be provided.

A separate by-subject listing of study drug administration and drug accountability will be provided by subject ID number and visit (in chronological order).

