b) Fisher's exact test for categorical efficacy response (eg, HIV-1 RNA < 50 copies/mL in US FDA-defined snapshot algorithm), where *trtgrp* is the treatment, and *response* is the categorical efficacy response. P-value from 2-sided Fisher's exact test should be used to test superiority.

```
proc freq data=adeff;
   tables trtgrp*response/fisher; /*p value from Fisher's exact test*/
run:
```

c) ANOVA model for continuous efficacy variable (eg, CD4):

The differences in changes from baseline in CD4 cell count between treatment groups and the associated 95% CI will be constructed using ANOVA, including the prior treatment regimen as fixed effects in the model.

SAS code is as follows:

```
proc glm data=adeffi;
  class trtgrp;
  model CD4 = trtgrp;
  lsmeans trtgrp /alpha=0.05 cl pdiff;
run;
```

Similar code will be used for the analysis of CD4 %.

d) Subgroup analyses

For the subgroups of age, race, sex, region and study drug adherence, p-value from 2-sided Exact method should be used to test superiority. The proportion difference between two treatment groups and 95% CIs are calculated based on an unconditional exact method using 2 inverted 1-sided tests, similarly to that for the primary efficacy endpoint.

14) Treatment-emergent AE (TEAE)

Events with Missing Onset Day and/or Month

The event is treatment emergent in a safety period, if the following 3 criteria are met:

- a) The month and year (or year) of onset date is the same as or after the month and year (or year) of the start date of the safety period, and
- b) The month and year (or year) of the onset date is the same as or before the month and year (or year) of safety cutoff date of the safety period, and
- c) AE end date is as follows:
 - i) The (complete) AE end date is on or after the safety period start date, or
 - ii) The month and year (or year) of end date is the same or after the month and year (or year) of the safety period start date, or
 - iii) AE end date is completely missing.

Events with Completely Missing Onset Date

An AE with a completely missing onset date is defined as TEAE for a safety period if AE end date meets any of the criteria specified in 3) above.

15) Renal related laboratory evaluation

Urine Protein Correction

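### A between-arm superiority test within HIV adherence strata conditions on a variable measured after randomisation, so it cannot be read as a treatment effect

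*SAP*

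**What the plan says.** SAP Section 3.4.1 lists HIV study drug adherence (below 95%, and 95% or more) among the subgroups for HIV-1 RNA below 50 copies/mL at Week 24, "based on adherence up to Post HCV Treatment Week 4 visit". Protocol Section 8.1.3 notes: "Most often, 24 weeks of HIV therapy will coincide with the Post-HCV Treatment Week 4 visit". SAP Section 6.2.2.2 runs the virologic response analysis in every Section 3.4.1 subgroup, on the HIV full analysis set.

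The method is in SAP Appendix 4, item 13d: "For the subgroups of age, race, sex, region and study drug adherence, p-value from 2-sided Exact method should be used to test superiority". The same item adds the difference in proportions between the two arms, with an unconditional exact 95% CI.

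SAP Section 4.2.2.1 calculates adherence from pill counts. Pills taken in a period is the smaller of the number prescribed and the "number of pills dispensed minus the number of pills returned". If a bottle came back but its count is missing, "it is assumed the number of pills returned was zero". If the dispensed count is missing, a bottle was not returned, or its return status is unknown, "all records for the same dispensing date for that study drug will be excluded from both denominator and numerator calculation".

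**The concern.** Randomisation balances the arms as a whole. It also supports comparisons within subgroups fixed beforehand, such as age, sex and race. Adherence is different: it is observed while subjects take the regimen being compared. The trial is open-label and the two regimens differ in components and interaction profile, so tolerability or adherence could differ by arm. The stratum at 95% or more may then hold different kinds of subject in each arm, and so may the stratum below 95%. A difference found there could come from who was selected into the stratum.

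At stake is the reading of one table that supports a secondary HIV endpoint. Item 13d labels the result a superiority test, so a reader of the report could take it as evidence that one regimen works better in adherent patients. SAP Section 3.5 discusses multiplicity for SVR12 only and gives no caution for this table.

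**Working it through.** The plan states no figure on this point, so there is none to reproduce.

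**1. Timing.** HIV drug starts at Day 1, after randomisation. Adherence for the subgroup runs from there to the Post-HCV Treatment Week 4 visit (SAP 3.4.1). The outcome window is Study Days 155 to 196 (SAP 6.2.2.2), and that visit usually falls at Week 24 (Protocol 8.1.3). SAP 4.2.2.1 also defines a Week 24 adherence that stops at dispensing records before Week 24. On either definition the stratifying variable accrues after randomisation and ends at about the time of the outcome.

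**2. What conditioning does.** Let *a* be the share of subjects who would reach 95% on either regimen, and *b* the share who would reach it only on regimen A. The upper stratum then holds *a* + *b* in arm A but only *a* in arm B. Suppose the regimen makes no difference to suppression, with rates *s_a* and *s_b* in the two kinds of subject. The expected difference in the stratum is

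(*a s_a* + *b s_b*)/(*a* + *b*) − *s_a* = *w*(*s_b* − *s_a*), where *w* = *b*/(*a* + *b*).

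This is zero only if *w* = 0 or the two rates are equal. As illustration, take *s_a* = 97% and *s_b* = 92%. These are the Week 48 suppression rates in two E/C/F/TAF switch studies described in Protocol 1.2.2, and assigning them to these groups is my assumption. The spurious difference is then −5*w* percentage points: from 0 when *w* = 0 towards −5 as *w* approaches 1. The documents give no information on *w*.

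**3. What the test could show.** I read the exact method in item 13d as Fisher's test, as in item 13b. Assume 40 to 60 subjects per arm in a stratum and a nominal two-sided 0.05, since no subgroup alpha is stated.

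| True rates | Probability of rejection |
|---|---|
| 97% in both arms | 0.07% to 0.32% |
| 92% in both arms | 1.2% to 1.8% |
| 97% versus 92% | 3.4% to 9.4% |

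The p-value would seldom be significant. Power is low, and a difference or CI distorted by selection stays distorted whether or not the p-value crosses 0.05.

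**4. The pill-count rule.** Inputs are one tablet daily (Protocol 5.3), 30-tablet bottles (Protocol 5.2.2), and dispensing at Day 1 and Weeks 4, 8, 12, 16 and 20 (Protocol 6.4.1 and Appendix 2). That gives 6 × 28 = 168 doses. An uncounted 28-day period scores min(28, 30 − 0) = 28 of 28. The 95% limit needs 0.95 × 168 = 159.6, so 160 taken and at most 8 missed. If uncounted periods were excluded instead:

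| Uncounted periods | Counted doses | Missed doses allowed, SAP rule | Missed doses allowed, exclusion |
|---|---|---|---|
| 1 | 140 | 8 | 7 (133/140 = 95.0%) |
| 2 | 112 | 8 | 5 (107/112 = 95.5%) |
| 3 | 84 | 8 | 4 (80/84 = 95.2%) |

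Now take a subject who took 14 of 28 in one uncounted period and missed nothing else. True adherence is 154/168 = 91.7%. The SAP rule gives 168/168 = 100% and exclusion gives 140/140 = 100%. The classification is wrong under both rules, so exclusion does not repair it.

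**The case against.** The strongest reply is that little hangs on this. The table supports a secondary HIV endpoint, the documents attach no hypothesis or alpha to it, and the body of the SAP does not use the word superiority for subgroups. Rejection by chance is rare in step 3. The wording may also be carried over: item 13d refers to a between-arm difference for the primary efficacy endpoint, although the primary analysis is a one-sample comparison with 88%. All of this stands and limits the importance of the point. It does not remove it, because the appendix is the current programming instruction and rare significance does not make a selected contrast a randomised one.

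A reader might draw four stronger conclusions that the documents do not support.

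- **The zero-returned rule materially overstates adherence.** It applies only when the site has confirmed the bottle's return, and reading a blank count as empty is a defensible convention. Protocol 5.5 requires returned quantities to be recorded, and SAP 2.2 requires queries to be resolved before the final analysis. The frequency of missing counts is not given. The rule does not always score 100%: a 32-day interval on one bottle gives 30/32 = 93.8%.
- **The two drugs' rules conflict.** For LDV/SOF, Section 4.2.2.2 says: "If a bottle is dispensed but not returned (missing), the number of tablets taken from that bottle will be counted as zero". That covers an unreturned bottle, which is a different situation from a returned one without a count.
- **Subgroup testing carries a large false-positive rate.** Eight levels (age, sex, race, adherence) at 0.05 give 1 − 0.95^8 = 33.7% under independence, but Fisher's test is far more conservative here.
- **Region is meaningless in this trial.** Protocol 5.2.2 allows for other participating countries and SAP 4.1.1 summarises enrolment by country. What the text supports is that Section 3.4.1 does not list region.

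**Conclusion.** The point holds for the between-arm contrast within the two HIV adherence strata. The strata are formed after randomisation, up to about the outcome visit, in an open-label comparison, and item 13d calls for a superiority p-value, a difference and a CI inside them. That contrast cannot be read as a treatment effect. The size of any bias cannot be computed from the documents. In the illustration it is −5*w* percentage points, with *w* unknown. The power range assumes 40 to 60 subjects per arm in a stratum.

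The consequence is small: one exploratory table is affected and SVR12 is not. The pill-count rule is a best-case assumption worth noting, but with one of six periods uncounted the alternative moves the limit by a single missed dose (8 against 7). The mention of region is a clerical mismatch.

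**What to change.** In SAP Appendix 4 item 13d, remove study drug adherence from the subgroups that receive a between-arm difference, CI and superiority p-value. Report HIV-1 RNA below 50 copies/mL in each adherence stratum as a within-arm proportion with an exact 95% CI, labelled descriptive. Delete region from item 13d so that it agrees with Section 3.4.1.

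The cost is a short edit to one SAP item and the loss of one exploratory between-arm contrast. No new data are needed, and the age, sex and race comparisons stay as planned. The pill-count rule can stay. Excluding records with a missing returned count would match the handling of the other gaps in Section 4.2.2.1, at the price of a few more excluded records, but this is optional.

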4.2.2.2. Adherence to LDV/SOF

The presumed total number of LDV/SOF tablets administered to a subject will be determined by the data collected on the drug accountability eCRF using the following formula:

Total Number of Doses Administered =
$$(\sum No. \text{ of } LDV/SOF \text{ Tablets Dispensed}) - (\sum No. \text{ of } LDV/SOF \text{ Tablets Not Administered})$$

The level of adherence to the study drug will be assessed based on the total amount of study drug administered relative to the total amount of study drug prescribed at LDV/SOF Day 1.

The level of adherence will be expressed in percentage using the following formula:

Level of Adherence (%) =
$$\left(\frac{\text{Total Amount of Study Drug Administered}}{\text{Total Amount of Study Drug Prescribed at Baseline}}\right) \times 100$$

Note: If calculated adherence is greater than 100%, the result will be set to 100%.

In this study, the total amount of LDV/SOF FDC (90 mg/400 mg) prescribed for 12 weeks will require 84 tablets.

Subjects who prematurely discontinue study drug for lack of efficacy (ie, virologic failure) will have the total amount of study drug prescribed calculated up to the first date when virologic failure criteria were met. For virologic failure confirmed by 2 consecutive measurements the date of the first measurement will be used. If there are study drug bottles dispensed on or after the subject first met virologic failure criteria, these bottles will not be included in the calculation of adherence. If a bottle is dispensed and the bottle is returned empty, then the number of tablets returned will be entered as zero. If a bottle is dispensed but not returned (missing), the number of tablets taken from that bottle will be counted as zero.

Descriptive statistics for the level of LDV/SOF adherence (n, mean, SD, median, Q1, Q3, minimum and maximum) with the number and percentage of subjects belonging to adherence categories (eg, < 80%, $\ge 80\%$ to < 90%, $\ge 90\%$) will be provided by treatment group and overall for the Part 2 Safety Analysis Set. No inferential statistics will be provided.

A separate by-subject listing of study drug administration and drug accountability will be provided by subject ID number and visit (in chronological order).

4.3. Protocol Deviations

A by-subject listing will be provided for those subjects who violate at least one inclusion or exclusion criterion (or criteria if more than 1 violation) that subjects did not meet and related comments, if collected.

Subjects who received the study drug other than their treatment assigned at randomization will be listed with the start and stop dates that they received incorrect study treatment.

5. BASELINE CHARACTERISTICS

5.1. Demographics

FTC/RPV/TAF

Subject demographic data (age, sex, race, and ethnicity) and baseline characteristics (body weight, height, BMI) will be summarized by treatment group and total at study baseline, using Safety Analysis Set; and by treatment group and total for each HCV genotype (1a, 1b, and other if applicable) and overall at Part 2 baseline, using Part 2 Safety Analysis Set. Continuous data will be summarized using descriptive statistics (n, mean, SD, median, Q1, Q3, minimum, and maximum) and categorical data will be summarized by the number and percentage of subjects. Age is calculated as age in years. In addition, age categories ($< 50, 50 - < 65, and \ge 65$ years) and BMI categories (< 30 and ≥ 30) will be summarized similarly.

In summary of demographic data at the study baseline, for continuous data, a 2-sided Wilcoxon rank sum test will be used to compare the two treatment groups; for categorical data, the Cochran-Mantel-Haenszel (CMH) test (general association statistic for nominal data and row means scores differ statistic for ordinal data) will be used to compare the two treatment groups.

